## 7.1.2. Safety

For analysis as per medDRA classification that combines solicited and unsolicited symptoms, the following lower level term will be used for the solicited symptoms:

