1.2. Rationale for the study and study design

1.2.1. Rationale for the study

Nearly 22,900 subjects received the active HZ/su study vaccine in clinical trials worldwide, most of whom (95%) were ≥ 50 YOA. Due to the high efficacy of the vaccine, most HZ and PHN cases were prevented, thus avoiding any negative impact on QoL in those subjects. No imbalance between the vaccine and the placebo arms were found in terms of SAEs, potential Immune-Mediated Diseases (pIMDs) or death during the entire duration of the studies. The vaccine was generally well tolerated. However, the vaccine was more reactogenic than placebo (saline solution).

In the pooled analysis of the ZOSTER-006 and ZOSTER-022 studies the most common side effects were at the site of injection, including pain, redness, and swelling. Up to 70% of people who received the HZ/su vaccine had pain at the injection site. These symptoms were usually mild and resolved within about 3 days on average. The incidence of grade 3 solicited local pain, was about 4%, with an average duration of less than 2 days. Grade 3 reactogenicity is defined as preventing ADL. Other side effects seen in more than 10% of people who received the vaccine included myalgia, fatigue, headache, shivering, fever

and gastrointestinal symptoms such as nausea, vomiting, diarrhoea and/or abdominal pain. The incidence of myalgia and fatigue was about 33% (overall/dose) and had an average duration of 2.5 days. The incidence of grade 3 solicited general symptoms was 3% or less (overall/dose) with average durations of less than 2 days. The reactogenicity is likely to be secondary to the enhanced innate immune responses elicited at the site of injection and therefore is expected [Didierlaurent, 2014]. This is consistently observed in studies evaluating AS01 – (and other) adjuvanted vaccines, in which higher reactogenicity is observed with adjuvanted versus non-adjuvanted vaccines [Stassijns, 2016].

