8.1.3.1. **Solicited local (injection-site) adverse events**

The following local (injection-site) AEs will be solicited:

Table 9 Solicited local adverse events

Pain at injection site
Redness at injection site
Swelling at injection site

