**Table 2 Lower level and preferred terms for solicited symptoms**

Solicited symptom	Lower level term name	LLT code	Corresponding Preferred Term name
Pain	Pain	10033371	Pain
Redness	Erythema	10015150	Erythema
Swelling	Swelling	10042674	Swelling
Fatigue	Fatigue	10016256	Fatigue
Fever	Fever	10016558	Pyrexia
Gastrointestinal symptoms	Gastrointestinal disorder	10017944	Gastrointestinal disorder
Headache	Headache	10019211	Headache
Myalgia	Myalgia	10028411	Myalgia
Shivering	Shivering	10040558	Chills

Note that for all tables described in this section, the way the percentage of subjects will be derived will depend on the event analysed (see table below for details). As a result, the N value will differ from one table to another.

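### SAP Table 2 codes solicited injection-site pain, redness and swelling to site-free MedDRA terms, so any combined solicited-plus-unsolicited MedDRA output loses the site (minor)

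*SAP*

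**What the plan says.** Protocol 8.1.3.1 (Table 9) lists the solicited local events with the site as part of the name: "Pain at injection site", "Redness at injection site", and swelling in the same form.

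SAP 7.1.2 gives a coding rule for one kind of output: "For analysis as per medDRA classification that combines solicited and unsolicited symptoms, the following lower level term will be used for the solicited symptoms". The table that follows, titled "Lower level and preferred terms for solicited symptoms", lists for each symptom the lower level term, its code and the preferred term. The three local rows read:

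- "Pain Pain 10033371 Pain"
- "Redness Erythema 10015150 Erythema"
- "Swelling Swelling 10042674 Swelling"

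None of these terms carries a site. Nothing in SAP 7.1.2 adds an injection-site flag or keeps solicited and unsolicited events in separate rows of such an output.

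SAP 6.6 lists the safety tabulations. Each solicited local and general symptom is tabulated individually. Solicited and unsolicited events are combined in one analysis that is split into local, general and any. Unsolicited events have their own table by preferred term, up to 30 days after each vaccination, repeated for grade 3 and for related events.

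**The concern.** For the three local symptoms, the site is what makes the event a vaccine reaction. Table 2 drops it, and the protocol and SAP treat the two kinds of event that then share a term differently:

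- **Causality.** Under protocol 8.3.3.2.2, every solicited local reaction counts as related to vaccination, while all other events are judged by the investigator. A merged row mixes automatic with judged relatedness.
- **Grading.** Under SAP 7.1.2.1, redness and swelling are graded by diameter, while unsolicited events are graded by interference with daily activities. A merged Erythema or Swelling row shown by grade mixes two scales.
- **Onset.** The protocol glossary makes a solicited symptom that starts outside the solicited period an unsolicited event. If that late event is coded with its site, the same reaction appears under different terms depending only on the day it began.

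At stake is whether a combined MedDRA table can be read on its own. Its Pain, Erythema and Swelling rows would consist largely of injection-site reactions without saying so.

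**Working it through.** **Text check.** The plan states no figure for this point, so there is none to reproduce.

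| Solicited event (protocol Table 9) | Preferred term (SAP Table 2) | Site kept? |
|---|---|---|
| Pain, injection site | Pain | No |
| Redness, injection site | Erythema | No |
| Swelling, injection site | Swelling | No |

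The general symptoms keep their meaning (for example fever to Pyrexia, shivering to Chills). Only the three local rows lose a defining attribute.

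**Illustration of the merging, for Pain.** Inputs:

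- s, proportion of subjects with solicited injection-site pain: 0.70. Protocol 1.2.1 says, of the pooled pivotal trials, "Up to 70% of people who received the HZ/su vaccine had pain at the injection site". This is an upper figure, so 0.50 and 0.30 are shown as well (assumed).
- u, proportion with an unsolicited event coded to Pain: assumed 0.01, 0.03 or 0.05. The documents give no value.
- N = 400, the target enrolment (protocol 4.1).
- The two events are assumed independent within subject.

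Formulas: combined row = s + (1 − s)u; subjects with unsolicited Pain = N·u; of these, already counted through injection-site pain = N·u·s.

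For s = 0.70 and u = 0.05: row = 0.70 + 0.30 × 0.05 = 0.715; subjects with unsolicited Pain = 400 × 0.05 = 20; already counted = 20 × 0.70 = 14.

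| s | u | Combined row | With unsolicited Pain | Already counted |
|---|---|---|---|---|
| 0.70 | 0.01 | 70.3% | 4 | 2.8 |
| 0.70 | 0.03 | 70.9% | 12 | 8.4 |
| 0.70 | 0.05 | 71.5% | 20 | 14 |
| 0.50 | 0.01 | 50.5% | 4 | 2 |
| 0.50 | 0.03 | 51.5% | 12 | 6 |
| 0.50 | 0.05 | 52.5% | 20 | 10 |
| 0.30 | 0.01 | 30.7% | 4 | 1.2 |
| 0.30 | 0.03 | 32.1% | 12 | 3.6 |
| 0.30 | 0.05 | 33.5% | 20 | 6 |

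Under independence the share absorbed equals s, so most unsolicited cases are absorbed only when s is above one half. Without independence, at s = 0.70 and u = 0.05, the row lies between 70% (all absorbed) and 0.70 + 0.05 = 75% (none absorbed). In either case the row mainly reflects the injection-site rate.

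The loss of site needs none of these assumptions. At u = 0 the row still reads 70% under the bare label Pain.

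**The case against.** The strongest reply is that the affected output is hardly specified. SAP 6.6 names no table by preferred term that merges solicited and unsolicited events. The combined analysis it does list is split by local and general and does not depend on Table 2. Row labels and footnotes belong to the separate tables annex, which is not among the documents. This stands as a limit on the size of the point. It does not remove it, because SAP 7.1.2 expressly provides for such an analysis and sets its coding.

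A reader might infer that a genuine systemic signal under these three terms would go unseen. The documents do not support that. Unsolicited events have their own table by preferred term, and serious events are tabulated separately and described in detail. What is obscured is obscured only in the combined output.

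A reader might also infer that local reactions are reported as general ones. That goes too far: Pain, Erythema and Swelling are silent about site, and SAP 6.6 carries the local/general classification separately. Nor can the Pain row be said to reach at least 70%, because the protocol gives that number as an upper figure.

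Finally, protocol 8.3.3.1 asks investigators to record a diagnosis, where one can be established, in place of individual symptoms. That makes unsolicited entries coded to bare Pain or Swelling less likely, so u may be small. This is fair, but it bears on how much merging occurs and not on the loss of site.

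**Conclusion.** The point holds in a limited form. Followed as written, Table 2 strips the site from three solicited local symptoms in combined MedDRA outputs and puts them in one row with any unsolicited event coded to the same term. The loss of site follows from the text alone. The amount of merging rests on an assumed unsolicited rate of 1% to 5%, on independence, and on an upper figure for injection-site pain; with those inputs the Pain row reads about 70% to 71.5%, with 70% of the unsolicited cases absorbed.

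The solicited, local/general and unsolicited-only tables are unaffected, as are the primary SF-36 PF endpoint and the QALY analysis. The study has one group and is descriptive, with no success criterion (protocol 10.7). Severity: minor.

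**What to change.** In SAP Table 2, replace the lower level term, code and preferred term of the three local symptoms with the site-specific (injection-site) terms of the MedDRA version used for the study. The codes should be taken from that version, which the documents do not state. Leave the six general symptoms unchanged. A bare Pain, Erythema or Swelling row would then no longer contain the solicited local reactions; in the illustration it would show the unsolicited rate alone, 1% to 5%.

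Cost: three rows of one table and the matching format catalogue. No new data are needed. It would also help to name the combined MedDRA table in SAP 6.6, so that a reader can see where the coding rule applies.

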**Table 2 Lower level and preferred terms for solicited symptoms**

Solicited symptom	Lower level term name	LLT code	Corresponding Preferred Term name
Pain	Pain	10033371	Pain
Redness	Erythema	10015150	Erythema
Swelling	Swelling	10042674	Swelling
Fatigue	Fatigue	10016256	Fatigue
Fever	Fever	10016558	Pyrexia
Gastrointestinal symptoms	Gastrointestinal disorder	10017944	Gastrointestinal disorder
Headache	Headache	10019211	Headache
Myalgia	Myalgia	10028411	Myalgia
Shivering	Shivering	10040558	Chills

Note that for all tables described in this section, the way the percentage of subjects will be derived will depend on the event analysed (see table below for details). As a result, the N value will differ from one table to another.

**Table 3 Details of calculation of percentages for each category of safety analysis**

Event	N used for deriving %	Terminology used in the tables for N
Concomitant medication	All vaccinated subjects	Number of subjects with at least one administered dose
Solicited general symptom	All vaccinated subjects with at least one solicited general symptom documented as either present or absent	For each dose and overall/subject: N= number of subjects with at least one documented dose For overall/dose: N= number of documented doses
Solicited local symptom	All vaccinated subjects with at least one solicited local symptom documented as either present or absent	For each dose and overall/subject: N= number of subjects with at least one documented dose For overall/dose: N= number of documented doses
Unsolicited symptom from day 0 to day X	All vaccinated subjects	Number of subjects with at least one administered dose
SAE	All vaccinated subjects	Number of subjects with at least one administered dose

# Statistical Analysis Plan

GlaxoSmithKline

Study alias & e-track number(s): ZOSTER-063 (204928)

- SAS date derived from a character date: In case day is missing, 15 is used. In case day & month are missing, 30June is used.
- Onset day for an event (ae, medication, vaccination, ...): The onset day is the number of days between the last study vaccination and the onset/start date of the event. This is 0 for an event starting on the same day as a vaccination. See SAS date derived in case the start date of the event is incomplete.
- Duration: Duration of an event is expressed in days. It is the number of days between the start and the stop dates + 1. Therefore duration is 1 day for an event starting and ending on the same day.
- Related dose: The related dose for an event (e.g., AE, medication, vaccination,...) is the study dose given before an event. In case the event takes place on a day a study dose is given, the related dose will be that of the study dose even if the event actually took place before. For instance, for a conc. medication started on the day of study dose 2 but before dose 2 administrations, the related dose will be dose 2.
- The confidence intervals will be exact 95% CIs for a proportion within a group calculated according to Clopper & al. (1934).

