# Statistical Analysis Plan

Study alias & e-track number(s): ZOSTER-063 (204928)

- Days 0 to 6 after each vaccination.
- Solicited local and general symptoms in subjects.
  - Occurrence, intensity and duration of solicited local symptoms within 7 days (Days 0-6\*\*) after each vaccination.
  - Occurrence, intensity, duration and relationship to vaccination of solicited general symptoms within 7 days (Days 0-6\*\*) after each vaccination.
- Unsolicited adverse events (AEs) in subjects.
  - Occurrence, intensity and relationship to vaccination during 30 days (Days 0-29) after each vaccination, according to the Medical Dictionary for Regulatory Activities (MedDRA) classification.
- Occurrence of serious adverse events (SAEs).
  - Occurrence and relationship to vaccination of all SAEs from the first vaccination up to the study end.
- Occurrence of adverse events of specific interest (AESIs): potential Immune-Mediated Diseases (pIMDs).
  - Occurrence and relationship to vaccination of any pIMDs from first vaccination up to the study end.

\*Note: baseline for dose 1 is defined as the mean of the assessments at day -7 and day 0; for dose 2 baseline is defined as the mean of the three assessments at day -7, day 0 and day 60 (day 0 for dose 2).

\*\*Note: The post-vaccination completion of SF-36 and EQ-5D questionnaires brought home by the subjects will be on days 1 to day 6, with day 7 to be filled in at the site (during Visits 3 and 5); while the post-vaccination recording of solicited AEs on the diary card brought home by the subjects will be on days 0 to day 6.

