# Statistical Analysis Plan

Study alias & e-track number(s): ZOSTER-063 (204928)

- Summary of temperature value by half degree increment taken reported during the 7-day (Days 0-6) post-vaccination period following each dose and overall doses and subjects **with no conversion rule**.
- Summary of temperature value by half degree increment **by route temperature** taken reported during the 7-day (Days 0-6) post-vaccination period following each dose and overall doses **with no conversion rule**.
- The number of days with each individual solicited local and general AE **during the solicited 7-day follow-up period** will be tabulated;
- The number of days with each solicited symptom local and general **during the whole post vaccination period** will be tabulated.
- The percentage of subjects with at least one local solicited AE, with at least one general solicited AE and with any solicited AE reported during the solicited 7-day follow-up period and **lasting beyond this period** will be tabulated with exact 95% CI after each vaccine dose and overall. The same tabulation will be performed for grade 3;
- The percentage of subjects with each individual solicited local and general symptoms **ongoing beyond the 7-day follow-up period** will be tabulated. The same tabulation will be performed for grade 3;
- The percentage of subjects with at least one report of unsolicited AE classified by the MedDRA Preferred Terms and reported up to 30 days after each vaccination will be tabulated with exact 95% CI. The same tabulation will be performed for grade 3 unsolicited AEs and for unsolicited AEs with a relationship to vaccination. The proportion of unsolicited AEs resulting in a medically attended visit (such as emergency room, out-patient visit, site investigator, etc.) will also be tabulated;
- Total number/percentages of doses followed by AEs will be tabulated;
- The percentage of subjects who started to use the medications within the 30-days post-vaccination will be tabulated.
- The percentage of subjects with at least one report of serious adverse event classified by the MedDRA Preferred Terms and reported during the whole post-vaccination follow up period will be tabulated with exact 95% CI;
- SAEs will be described in details;
- The proportion of subjects with at least one report of pIMDs classified by the MedDRA Preferred Terms and reported during the whole post-vaccination period (from dose 1 up to study end) will be tabulated with exact 95% CI.

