**HEADACHE**

1.\* Occurred?

**2**

[HE\_YN]  
[A:N]  No  
[A:Y]  [SYMP\_VAL\_INTEN]  
Yes -> [SYMP\_VAL\_INTEN\_D0] [SYMP\_VAL\_INTEN\_D1] [SYMP\_VAL\_INTEN\_D2] [SYMP\_VAL\_INTEN\_D3] [SYMP\_VAL\_INTEN\_D4] [SYMP\_VAL\_INTEN\_D5] [SYMP\_VAL\_INTEN\_D6]  
Intensity: Day 0: [INTENSITYSOL] Day 1: [INTENSITYSOL] Day 2: [INTENSITYSOL] Day 3: [INTENSITYSOL] Day 4: [INTENSITYSOL] Day 5: [INTENSITYSOL] Day 6: [INTENSITYSOL]  
[SYMP\_TM]  
Symptom first onset time: [Req/Unk] : [Req/Unk] 24-hour clock  
[HE\_ONG]  
After Day 6: Ongoing? [A:N]  No  
[A:Y]  [SYMP\_ONG\_INTEN]  
Yes -> [SYMP\_MAX\_INTEN]  
Maximum intensity: [INTENSITYSOLMAX]  
[ERDAT]  
Date of last day of sign/symptom: [Req/Unk] / [Req/Unk] / [Req/Unk] (2016-2018)  
[CONT\_END]  
Continuing at the end of the study? [A:Y]   
[CAUSAL]  
Is there a reasonable possibility that the AE may have been caused by the investigational product? [A:Y]  Yes  
[A:N]  No

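### SAP 7.1.2 completes partial event dates without checking them against known dates, so such an event can get a pre-dose onset, the wrong dose or window, or a non-positive duration (minor)

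*SAP*

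**What the plan says.** The derivation rules are in SAP 7.1.2, after Table 3.

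- **Partial dates:** "In case day is missing, 15 is used. In case day & month are missing, 30June is used".
- **Onset day:** "The onset day is the number of days between the last study vaccination and the onset/start date of the event". For incomplete start dates the SAP points back to the partial-date rule: "See SAS date derived in case the start date of the event is incomplete".
- **Related dose:** it "is the study dose given before an event", so it follows date order.
- **Duration:** "It is the number of days between the start and the stop dates + 1", with no lower limit.

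These derivations serve several outputs. SAP 4.2 defines the unsolicited AE endpoint as "Occurrence, intensity and relationship to vaccination during 30 days (Days 0-29) after each vaccination". SAP 6.6 tabulates AEs by time since the last vaccination and medications started within 30 days. It also tabulates "The number of days with each solicited symptom local and general" over the whole post-vaccination period, separately from the Day 0-6 table. For a symptom still present after Day 6, the eCRF screens in SAP Figures 2 to 4 ask for the "Date of last day of sign/symptom" and show an unknown option for each part of that date.

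Neither document compares a completed date with the dose date, the known start or the known stop. SAP 7.1.1 admits an inconsistency from date completion for age only. SAP 7.2.2 deals with missing measurements, not with the order of dates.

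**The concern.** The rule ignores facts that the record already holds. If an AE is recorded as following a dose on 20 March and its date is known only as March, it cannot have begun on 15 March, yet that is the date it receives. No study dose precedes that date, so related dose is undefined and the event drops out of Days 0-29. A symptom recorded as ongoing after Day 6 cannot have stopped before Day 7, yet the rule can make it do so.

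At stake are the Day 0-29 unsolicited AE percentages, their split between doses 1 and 2, the table of newly started medications, and the whole-period symptom durations. If nothing is written down, impossible values will have to be handled case by case after the data are seen.

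**Working it through.** **The plan's own figure.** Duration = stop - start + 1. For an event that starts and ends on 20 March, 20 - 20 + 1 = 1 day, as SAP 7.1.2 states.

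**Single cases from the written rules (2017 dates)**

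| Case | Completed date | Result |
|---|---|---|
| Dose 1 on 20 March; true onset 22 March, day missing | 15 March | Onset day 15 - 20 = -5; no preceding dose |
| Dose 1 on 21 March, dose 2 on 20 May (60 days apart); true onset 22 May, day missing | 15 May | Precedes dose 2, so assigned to dose 1 at Day 55; outside Days 0-29 |
| Symptom onset 20 March, last day known only as March | 15 March | Duration 15 - 20 + 1 = -4 days |

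**How often, given a missing day.** The documents give no distribution of dates, so these are assumptions: dose dates uniform over the 365 days of 2017, and true onset uniform over the stated range. Each result is an exact count over all combinations.

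*Onset on Days 0-29* (365 x 30 = 10,950 combinations):
- before the dose: 1,523 / 10,950 = 13.9%
- within Days 0-29: 8,167 / 10,950 = 74.6%
- after Day 29: 1,260 / 10,950 = 11.5%

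The 13.9% for dose 2 events is also the share moved to dose 1. It is the same for dose gaps of 49, 60 and 83 days (the protocol Table 6 range is 49 to 83, with 60 optimal).

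*Movement into the window:*
- true onset on Days 30-59, dated within Days 0-29: 1,523 / 10,950 = 13.9%
- medication started on Days -7 to -1, dated within Days 0-29: 924 / (365 x 7 = 2,555) = 36.2%

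*Solicited symptoms starting on Days 0-6 and ending on Days 7-13, stop day missing* (365 x 7 x 7 = 17,885 combinations):
- duration of zero or less: 4,949 / 17,885 = 27.7%
- stop date before Day 7, against the record: 7,301 / 17,885 = 40.8%

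**Day and month both missing.** With 30 June, 46.4% of true Day 0-29 onsets fall before the dose, 8.2% in the window and 45.3% after Day 29.

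**Effect of bounding.** When only the day is missing, every onset dated before the dose lies in the dose's own calendar month. Using the dose date there reduces 13.9% to 0. The 11.5% dated after Day 29 remain, so total loss from the window falls from 25.4% to 11.5%. Holding the stop date at Day 7 or later gives a symptom that starts on Day 6 at least 7 - 6 + 1 = 2 days, so no duration is zero or negative.

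**The case against.** The strongest reply is that little depends on this rule, and most of that reply stands.

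- **Solicited onset is safe.** Symptoms on Days 0-6 are entered on a per-dose day grid (SAP Figures 2 to 4), so their onset, dose and window cannot shift. The secondary duration endpoint in SAP 4.2 is limited to Days 0-6. Only the additional whole-period table is exposed, and only for symptoms ongoing after Day 6 with an unknown end day.
- **Partial onset dates should be uncommon.** Unsolicited AEs and medications are recorded daily on a card issued after each dose and reviewed with the subject (protocol 5.3.1.1 and 5.5.2.10). Omissions can be queried and entries verified (protocol 11.1 and 11.2). Queries cannot recover a date that the subject does not know, however, and they do not govern a derived date.
- **Impact is limited.** The analyses are descriptive (protocol 10.7). The percentages count subjects with at least one event, so one misdated event need not change them.

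A reader might also infer more than the documents support:

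- **That AE percentages are biased downward.** Events also move in. Serious AEs are collected for about 12 months after the last dose (protocol 8.3.1) and medications from 7 days before dose 1 (protocol 6.5.1), so those tables can be inflated.
- **That the eCRF is shown to accept unknown AE onset dates.** The unknown option for date parts appears only for the end date of solicited symptoms. No unsolicited AE or medication form is shown. SAP 7.1.2 does anticipate incomplete start dates, but that is all the evidence there is.
- **That about 92% of events can leave the window.** This is the year-only case (46.4% + 45.3%, before rounding). It needs an event from a 30-day daily diary whose month nobody can recall, which should be very rare.

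**Conclusion.** The gap is real and minor. As written, SAP 7.1.2 can give an event with a partial date an onset before its dose, the wrong dose, the wrong side of the Day 0-29 limit, or a zero or negative whole-period duration. The last point assumes that the whole-period table uses the SAP's duration formula with the recorded end date; no other rule is given.

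The sizes are 13.9% before the dose, 11.5% after Day 29 and about 28% non-positive durations. All are conditional on a missing day and on the uniform assumptions above. None estimates the change in a reported table, because the number of partial dates is not given and is probably low. The net direction of bias in the AE and medication percentages is not fixed.

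Solicited onset, the Day 0-6 solicited endpoints, and the primary and quality-of-life endpoints are not affected. For the questionnaires, SAP 7.1.3.1 treats an undated form as not evaluable instead of completing its date.

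**What to change.** Keep the 15th and 30 June as defaults in SAP 7.1.2, but bound them by what the record shows:

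1. For an AE recorded as post-vaccination, use the dose date if the completed onset would precede the dose and the known month or year contains the dose date.
2. Take the related dose from the dose-specific diary card or eCRF visit where available. Do not take it from the completed date, and do not default to the latest dose: with only the year known, that would send dose 1 events to dose 2.
3. Never set a stop date before the start date, nor before Day 7 when the symptom is recorded as ongoing after Day 6.
4. Do not move a medication start to the dose date unless the record shows that it began after vaccination. Otherwise, medication already in use would be counted as newly started.

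The cost is one SAP paragraph and a few lines of derivation code, with no new data, ideally before database freeze. AE percentages may change slightly in either direction. Some window error remains: under the assumptions above, 11.5% of day-missing onsets would still be dated after Day 29.
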